Secondary Objectives (Efficacy): To demonstrate the superiority of belantamab mafodotin compared to pomalidomide plus low dose dexamethasone (pom/dex) in ORR/CBR/TTR/TTP/DoR/MRD in participants with relapsed/refractory multiple myeloma (RRMM) [1]	Primary	ORR	ITT	
 
New anti-cancer therapy: while on treatment
 
Treatment discontinuation: treatment policy
 
	>=PR percentage by treatment arm
		CBR	ITT	
 
New anti-cancer therapy: while on treatment
 
Treatment discontinuation: treatment policy
 
	>=MR percentage by treatment arm
		DoR	ITT	
 
Disease assessments between scheduled visits: treatment policy
 
New anti-cancer therapy: while on treatment
 
Extended loss to follow-up: while on treatment
 
Treatment discontinuation: treatment policy
 
Death due to non-PD: composite
 
Death due to PD: composite
 
	Summarized using the Kaplan-Meier method by treatment arm
		TTR	ITT	
 
New anti-cancer therapy: while on treatment
 
Treatment discontinuation: treatment policy
 
	Descriptive summary of TTR by treatment arm
		TTP	ITT	
 
Disease assessments between scheduled visits: treatment policy
 
New anti-cancer therapy: while on treatment
 
Extended loss to follow-up: while on treatment
 
Treatment discontinuation: treatment policy
 
Death due to non-PD: while on treatment
 
Death due to PD: composite
 
	Hazard ratio for belantamab mafodotin vs pom/dex
		MRD	ITT	
 
New anti-cancer therapy: while on treatment
 
Treatment discontinuation: treatment policy
 
	MRD negativity percentage by treatment arm
	Supplementary	DoR	ITT	
 
Disease assessments between scheduled visits: treatment policy
 
New anti-cancer therapy: while on treatment
 
Extended loss to follow-up: while on treatment
 
Treatment discontinuation: treatment policy
 
Death due to non-PD: while on treatment
 
Death due to PD: composite
 
	Summarized using the Kaplan-Meier method by treatment arm

Objective	Estimand Category	Estimand			Population Level Summary Measure
		Variable/Endpoint	Analysis Set	Intercurrent Event Strategy	

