### 4.2.2. Planned analysis of PFS

#### Overview of the planned analyses

- Primary analysis of PFS will be based on investigator-assessed response (per IMWG Kumar, 2016)
- Handling of intercurrent events for primary estimand (Table 1) are specified as the primary event and censoring rules in Table 2; Handling of intercurrent events for supplementary estimands 1&2 (Table 1) are specified as the alternative event and censoring rules 1&2 in Table 2, respectively;

The following sets of analyses will be conducted:

- [1]. Primary analysis of primary estimand ( investigator-assessed response + primary censoring rules);
- [2]. Primary analysis of supplementary estimand 1 ( investigator-assessed response + alternative censoring rules 1);
- [3]. Primary analysis of supplementary estimand 2 ( investigator-assessed response + alternative censoring rules 2);

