##### ***Definition of Endpoint(s)***

At final PFS/OS analysis, the analyses for the following supportive secondary efficacy endpoints will be conducted:

- **Overall response rate (ORR)**, is defined as the percentage of participants with a confirmed PR or better (i.e., PR, VGPR, CR, and sCR).
- **Clinical benefit rate (CBR)**, is defined as the percentage of participants with a confirmed minimal response (MR) or better.  
ORR and CBR will be analyzed based on the confirmed responses, which will be derived based on the algorithm specified in Table 3. Only the assessments from the start of treatment up to the earlier of confirmed disease progression or the start of new anti-cancer therapy will be considered. Only new systemic anti-cancer drugs taken are considered as anti-cancer therapy (radiotherapy and surgeries are not considered as systemic anti-cancer therapy for the purpose of this analysis). Participants with only assessments of Not Evaluable or missing response will be treated as non-responders; i.e. they will be included in the denominator when calculating the percentage.
- **Duration of response (DoR)** is defined as the time from first documented evidence of PR or better until the earliest date of disease progression (PD), or death due to any cause among participants who achieve a response (i.e., confirmed PR or better). Responders without disease progression will be censored at the censoring time point for PFS.
- **Time to response (TTR)** is defined as the time between the date of randomization and the first documented evidence of response (PR or better), among participants who achieve a response (i.e., confirmed PR or better).

- **Time to progression (TTP)** is defined as the time from randomization until the earliest date of PD, or death due to PD. Determination of dates of TTP event and dates for censoring are described in the [Table 4](#).
- **Minimal Residual Disease (MRD) Negativity Rate**, is defined as: the percentage of participants who are MRD negative by Next Generation Sequencing (NGS).

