**Table 4 Assignments for Progression and Censoring Dates for TTP Analysis**

Situation	Date of Event (Progression/Death) or Censoring	Outcome Event (progression/Death) Or Censored
No ( or inadequate ) baseline tumor assessments  and the subject has not died (if the subject has died follow the rules for death indicated at the bottom of the table)	Randomization	Censored
No post-baseline assessments and the subject has not died (if the subject has died follow the rules for death indicated at the bottom of the table)	Randomization	Censored
Progression documented at or between scheduled visits, without extended loss-to-follow-up time 	Date of assessment of progression	Event
No progression ( or death )	Date of last 'adequate' assessment of response 	Censored
New anticancer treatment started ( prior to documented disease progression or death )  .	Date of last 'adequate' assessment of response  ( on or prior to starting anti-cancer therapy )	Censored
Death due to progression without extended loss-to-follow-up time 	Date of death	Event
Death from causes other than progression without extended loss-to-follow-up time 	Date of death	Censored
Death or progression after an extended loss-to-follow-up time 	Date of last 'adequate' assessment of response  prior to PD/death ( prior to missed assessments )	Censored
Death or progression after an extended loss-to-follow-up time  from randomization	Date of randomization	Censored

[1]. Adequate baseline assessment is defined as at baseline, a patient has at least one of the following measurements: a. Serum M-protein  $\geq 0.5$  g/dL ( $\geq 5$  g/L) or b. Urine M-protein  $\geq 200$  mg/24h or c. Serum FLC assay: Involved FLC level  $\geq 10$  mg/dL ( $\geq 100$  mg/L) and an abnormal serum free light chain ratio ( $<0.26$  or  $>1.65$ )

Situation	Date of Event (Progression/Death) or Censoring	Outcome Event (progression/Death) Or Censored
-----------	--	---

- [2]. An adequate assessment is defined as an assessment where the response is sCR, CR, VGPR, PR, MR, or SD.

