**Main Analytical Approach**

- **ORR:** The number and percentage of participants with the best confirmed response in the following response categories at will be summarized by treatment arm: sCR, CR, VGPR, PR, overall response (sCR+CR+VGPR+PR), minimal response (MR), stable disease (SD), progressive disease (PD), and not evaluable (NE). The corresponding exact 95% CI for ORR will also be provided. Participants with unknown or missing responses will be treated as non-responders, i.e., these participants will be included in the denominator when calculating percentages of response. The exact 95% CI for the difference will be calculated.
- **CBR:** summaries of CBR by treatment arms will be provided in the same way as ORR.
- **DoR:** Distribution of DoR will be summarized using the Kaplan-Meier method by treatment arm. The median, 25th and 75th percentiles of DoR will be estimated and corresponding 95% confidence intervals will be estimated using the Brookmeyer-Crowley method [Brookmeyer, 1982].
- **TTR:** TTR will be summarized descriptively by treatment arm using medians and quartiles in the subset of participants with a confirmed response of PR or better as the Best Overall Response (BOR).
- **TTP:** Distribution of TTP will be summarized using the Kaplan-Meier method by treatment arm. The median, 25th and 75th percentiles of TTP will be estimated and corresponding 95% confidence intervals will be estimated using the Brookmeyer-Crowley method [Brookmeyer, 1982]. TTP analysis will also be conducted using Cox proportional hazards model stratified by randomization factors. Refer to Section 4.2.3 for details of the analytical approaches.
- **MRD Negativity Rate:** For MRD negativity rate based on bone marrow testing using Next Generation Sequencing (molecular negativity), the number and percentage of participants who have achieved MRD negativity will be summarized by treatment arm. For analysis purposes, participants in the ITT population without MRD assessment will be considered as having positive MRD. The corresponding exact 95%

CI for MRD negativity rate will also be provided. Number and percentage of participants who have sustained MRD negativity ( $\geq 6$  months,  $\geq 12$  months) will be provided. Information of MRD will be included in the listing of response. If data are available, imaging-based assessment of MRD (i.e. PET-CT) will also be included in the listing and related to NGS testing.

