### 5.2. Sample Size Determination

#### Primary Endpoint PFS

Based on available data from literature, the median PFS in the pom/dex arm is expected to be around 4 months [[San Miguel, 2013](#)]. It is expected that treatment with belantamab mafodotin will result in a 43% reduction in the hazard rate for PFS, i.e. an expected HR of 0.57 (corresponding to an increase in median PFS from 4 months to 7 months under the exponential model assumption).

The final PFS analysis will be conducted at the time of observing approximately 151 events and the first 320 randomized subjects have been followed for a minimum of 4 months. With 151 events, the study has a power of 90% to detect a hazard ratio of 0.57 at 1-sided alpha of 0.025 (corresponding to a critical value of 0.713 for the hazard ratio). This calculation assumes participants randomized to the two treatment arms in a 2:1 ratio. Assuming that enrolment will continue for approximately 20 months at a uniform rate of 16 participants per month, a total of 320 participants will be randomized in a 2:1 ratio to receive single agent belantamab mafodotin or pom/dex. It is estimated that the targeted 151 PFS events will be observed approximately 23 months after the first participant is randomized based on a lognormal cure rate model ([Chen, 2016](#)). These calculations were made using the software package East 6.5 and a proprietary SAS macro.

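### Kaplan-Meier summaries of TTP and supplementary DoR censor non-PD deaths, so they overstate progression risk; the TTP hazard ratio is unaffected

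*SAP*

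**What the plan says.** - **Definition.** SAP section 4.3.2.1 defines TTP as "the time from randomization until the earliest date of PD, or death due to PD". A death from any other cause is therefore not a TTP event.
- **Censoring.** Table 4 has a row for "Death from causes other than progression without extended loss-to-follow-up time", and its outcome is censoring at the date of death.
- **Description.** Under Main Analytical Approach, "Distribution of TTP will be summarized using the Kaplan-Meier method by treatment arm", with the median and the 25th and 75th percentiles.
- **Comparison.** "TTP analysis will also be conducted using Cox proportional hazards model stratified by randomization factors".
- **Estimand, TTP.** Table 1 (section 1.1.2) sets "Death due to non-PD: while on treatment" and names the summary measure as "Hazard ratio for belantamab mafodotin vs pom/dex".
- **Estimand, supplementary DoR.** Table 1 gives non-PD death the same label, but the only summary measure is a Kaplan-Meier summary by arm. Section 4.3.2.2 says that this estimand will be analysed and adds no other method.

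The TTP and DoR text names no cumulative incidence or other competing-risk summary.

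**The concern.** Death from another cause is a competing event for progression, because it makes progression impossible. Kaplan-Meier with such deaths censored assumes that the people who died would have gone on to progress at the same rate as those still at risk. That is a hypothetical-type quantity. The SAP keeps *hypothetical* as a separate label: in Table 1 it uses it for between-visit assessments in the first supplementary PFS estimand.

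What is at stake is how the descriptive results are read. A reader of a TTP curve will take its complement as the chance of having progressed by a given month. That reading is too high, more so as follow-up lengthens and as non-PD deaths become more common. The upper quartile is affected more than the median. For the supplementary DoR there is no hazard ratio beside the curve, so the descriptive result is the whole analysis.

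**Working it through.** **Inputs.** From SAP section 5.2: "the median PFS in the pom/dex arm is expected to be around 4 months", 7 months with belantamab mafodotin, an exponential model, HR 0.57, 2:1 allocation, 151 events, 90% power and one-sided alpha 0.025. The SAP does not give the share *q* of PFS events that are non-PD deaths. I assume 5% to 20%, equal in the two arms.

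**The plan's own figure.** Schoenfeld's formula gives (1.960 + 1.282)² / [(2/9) × (ln 0.57)²] = 10.51 / 0.0702 = 149.6, so 150 events against the stated 151. With 151 events the power is 90.3% and the critical HR is exp(-1.960 / √(151 × 2/9)) = 0.713, as stated. The PFS inputs are therefore coherent. The SAP has no figure for TTP to reproduce.

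**Formulas.** Let L = ln 2 / median PFS, and assume constant hazards.

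- Kaplan-Meier complement, non-PD deaths censored: 1 - exp(-(1-q)Lt)
- Cumulative incidence of PD or PD death: (1-q)(1 - exp(-Lt))

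**At 12 months.** exp(-Lt) is 0.125 for pom/dex (three half-lives) and 0.305 for belantamab mafodotin. Example, pom/dex, q = 10%: 1 - 0.125^0.9 = 84.6%, against 0.9 × 0.875 = 78.8%.

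| q | Pom/dex: 1-KM | Incidence | Excess (points) | Belantamab: 1-KM | Incidence | Excess (points) |
|---|---|---|---|---|---|---|
| 5% | 86.1% | 83.1% | 3.0 | 67.7% | 66.0% | 1.6 |
| 10% | 84.6% | 78.8% | 5.9 | 65.7% | 62.6% | 3.1 |
| 20% | 81.1% | 70.0% | 11.1 | 61.3% | 55.6% | 5.7 |

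Excesses are taken from unrounded values. Over the same range of q they are 1.3-4.8 (pom/dex) and 0.6-2.0 (belantamab mafodotin) at 6 months, and 4.0-15.3 and 2.6-9.4 at 18 months.

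**Quartiles at q = 10%.** The Kaplan-Meier median is ln 2 / (0.9L). The time to 50% cumulative incidence is -ln(1 - 0.5/0.9) / L. For the third quartile the two are ln 4 / (0.9L) and ln 6 / L.

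| | Pom/dex: KM | Pom/dex: incidence | Belantamab: KM | Belantamab: incidence |
|---|---|---|---|---|
| Median (months) | 4.44 | 4.68 | 7.78 | 8.19 |
| Third quartile (months) | 8.9 | 10.3 | 15.6 | 18.1 |

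**Hazard ratio.** In a constant-hazard simulation with 300,000 participants, q = 10% and follow-up cut at 18 months, I took the ratio of PD rates per person-time with non-PD deaths censored. Under constant hazards this targets the same quantity as the Cox model. It was 0.568, and 0.567 with the non-PD death hazard tripled in the belantamab mafodotin arm, against a true 4/7 = 0.571. Censoring the competing deaths leaves the cause-specific HR where it should be.

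**The case against.** **A contradiction between Table 1 and Table 4 for TTP.** A reader might infer one, but the documents do not support it. Table 1's summary measure for TTP is a hazard ratio, and the Cox model supplies it among people still alive and progression-free. That is compatible with *while on treatment*. The SAP also implements this label by censoring elsewhere: for PFS, "Handling of intercurrent events for primary estimand (Table 1) are specified as the primary event and censoring rules in Table 2", and Table 2 censors at new anti-cancer therapy and after extended loss to follow-up. This objection stands for TTP.

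It does not carry over to the supplementary DoR. Following the SAP's censoring convention does not change what the resulting curve estimates, and there the curve is the only summary. The SAP has no censoring table for DoR, so censoring at non-PD death there is inferred from the label and from its use for TTP.

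**A distorted comparison between arms.** This is not shown either. With an equal share in both arms, the ratio of third quartiles is about 1.75 on either scale (15.6/8.9 and 18.1/10.3). Unequal shares would be needed, and the SAP gives none.

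**The size.** The SAP plans no 12-month TTP rate. The only landmark that its cross-reference to section 4.2.3 could bring in is 6 months, where the excess is smaller. At q = 10% the median shifts, 0.24 and 0.41 months, are less than the three-week assessment interval (21/30.4 = 0.69 months). At q = 20% they are 0.66 (5.00 to 5.66) and 1.16 (8.75 to 9.91). The third quartiles lean on an exponential model, whereas section 5.2 projects event timing from a lognormal cure rate model. These limits are fair. They reduce the practical weight but not the direction of the error.

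**Other endpoints.** PFS and the primary DoR count every death, so non-PD deaths are not lost from the report.

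**Conclusion.** The point holds for the descriptive TTP results and for the supplementary DoR. The TTP Kaplan-Meier curve and its quartiles describe a setting without non-PD death, so they are not a reading of progression risk. For the supplementary DoR the Kaplan-Meier summary also does not fit the strategy that Table 1 gives to non-PD death.

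The direction is certain whenever such deaths occur. The size is conditional on an assumed 5-20% non-PD share and exponential PFS, and it is small if such deaths are rare.

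The definition of TTP is not at fault; the relevant text is Table 4 together with the Kaplan-Meier method. The TTP hazard ratio stands. Both endpoints are supportive and outside the hierarchy in section 2.1, so the PFS and OS tests are untouched. The point is minor. It is worth acting on because the remedy is cheap.

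**What to change.** - In section 4.3.2.1, add the cumulative incidence of PD or PD death by arm for TTP: Aalen-Johansen estimator, non-PD death as the competing event, 95% CI, at for example 6, 12 and 18 months.
- In section 4.3.2.2, add the same for the supplementary DoR, counted from first response among responders, and name it in the summary-measure column of that Table 1 row.
- Label the TTP Cox result a cause-specific hazard ratio.
- Keep the Kaplan-Meier quartiles, with a note that they treat non-PD death as censoring. Replacing them is not needed and would make comparison with published TTP results harder.

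The cost is SAP wording and one extra output per endpoint. No new data are required, since Table 4 already separates deaths due to progression from other deaths.

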**Table 3 Response confirmation algorithm based on visit-level response**

#	Response at the First Time Point	Response at Subsequent Disease Assessment 	Confirmed Response at the First Time Point
1	sCR	sCR	sCR
2	sCR	CR	CR
3	CR	sCR/CR	
4	sCR/CR	VGPR	VGPR
5	VGPR	sCR/CR/VGPR	
6	sCR/CR/VGPR	PR	PR
7	PR	sCR/CR/VGPR/PR	
8	sCR/CR/VGPR/PR	MR	MR
9	MR	sCR/CR/VGPR/PR/MR	
10	sCR/CR/VGPR/PR/MR	SD	SD
11	sCR/CR/VGPR/PR/MR	PD (any reason)  OR No subsequent disease assessment: subject died or discontinued study or started new anti-cancer therapy before further adequate disease assessment	SD
12	PD (due to reasons other than imaging, i.e., plasmacytoma or bone lesion)	PD (any reason) including PD after initiation of new anti-cancer therapy  OR No subsequent disease assessment: subject died due to PD before further adequate disease assessment and within 49 days of PD at First Time Point (including death due to PD after initiation of new anti-cancer therapy)	PD
13	PD (due to reasons other than imaging, i.e., plasmacytoma or bone lesion)	sCR/CR/VGPR/PR/MR/SD  OR No subsequent disease assessment: subject died due to reasons other than	NE

#	Response at the First Time Point	Response at Subsequent Disease Assessment 	Confirmed Response at the First Time Point
		
PD before further adequate disease assessment
 
OR
 
No subsequent disease assessment: subject discontinued study before further adequate disease assessment
	
14	sCR/CR/VGPR/PR/MR/PD (due to reasons other than imaging, i.e., plasmacytoma or bone lesion)	No subsequent disease assessment: subject has not died, discontinued from study or (except for PD) started new anti-cancer therapy; but as yet has no further adequate disease assessments	
Unconfirmed sCR/CR/VGPR/PR/MR/PD.
 
Will be categorized as NE for final ORR analysis.

15	SD	
Any
 
OR
 
No subsequent disease assessment
	SD
16	PD due to imaging (plasmacytoma or bone lesion)	
Any
 
OR
 
No subsequent disease assessment
	PD
17	NE or missing	
Any
 
OR
 
No subsequent disease assessment
	NE

1. Subsequent disease assessment is defined as the next adequate (not missing or NE) disease assessment following the first timepoint before (or on the same date of) start of new anti-cancer therapy except for confirmation of PD, for which PD or death due to PD after new anti-cancer therapy are considered for confirmation of PD. No minimal time interval is required for the subsequent disease assessment, but a different sample is required for confirmation.
2. SD does not need to be confirmed.
3. PD due to imaging (i.e., plasmacytoma or bone lesion) does not need to be confirmed.
4. Where criteria are not mutually exclusive, take the first that applies.

**Table 4 Assignments for Progression and Censoring Dates for TTP Analysis**

Situation	Date of Event (Progression/Death) or Censoring	Outcome Event (progression/Death) Or Censored
No ( or inadequate ) baseline tumor assessments  and the subject has not died (if the subject has died follow the rules for death indicated at the bottom of the table)	Randomization	Censored
No post-baseline assessments and the subject has not died (if the subject has died follow the rules for death indicated at the bottom of the table)	Randomization	Censored
Progression documented at or between scheduled visits, without extended loss-to-follow-up time 	Date of assessment of progression	Event
No progression ( or death )	Date of last 'adequate' assessment of response 	Censored
New anticancer treatment started ( prior to documented disease progression or death )  .	Date of last 'adequate' assessment of response  ( on or prior to starting anti-cancer therapy )	Censored
Death due to progression without extended loss-to-follow-up time 	Date of death	Event
Death from causes other than progression without extended loss-to-follow-up time 	Date of death	Censored
Death or progression after an extended loss-to-follow-up time 	Date of last 'adequate' assessment of response  prior to PD/death ( prior to missed assessments )	Censored
Death or progression after an extended loss-to-follow-up time  from randomization	Date of randomization	Censored

[1]. Adequate baseline assessment is defined as at baseline, a patient has at least one of the following measurements: a. Serum M-protein  $\geq 0.5$  g/dL ( $\geq 5$  g/L) or b. Urine M-protein  $\geq 200$  mg/24h or c. Serum FLC assay: Involved FLC level  $\geq 10$  mg/dL ( $\geq 100$  mg/L) and an abnormal serum free light chain ratio ( $<0.26$  or  $>1.65$ )

Situation	Date of Event (Progression/Death) or Censoring	Outcome Event (progression/Death) Or Censored
-----------	--	---

- [2]. An adequate assessment is defined as an assessment where the response is sCR, CR, VGPR, PR, MR, or SD.
- [3]. If PD or death and New anti-cancer therapy occur on the same day assume the progression or death was documented first (e.g., outcome is progression or death and the date is the date of the assessment of progression or death). If anti-cancer therapy is started prior to any adequate assessments, censoring date should be the date of randomization.
- [4]. Extended loss-to-follow-up time = 6 weeks + 7 day window = 49 day window; Without extended loss-to-follow-up time is defined as: <= 49 days; after an extended loss-to-follow-up time is defined as: >49 days. More details about extended loss-to-follow-up time are provided in Section 6.2.9.

